Phase Ia: Safety study of a single bladder instillation of probiotic in adults. A subsample of healthy adults with neuropathic bladder who do not have urinary symptoms meeting the criteria for antibiotic treatment of urinary tract infection or initiation of the protocol will undergo a single intravesicular instillation of *Lactobacillus* to determine the tolerability of the instillation, safety of a single instillation, and whether the instilled *Lactobacillus* persists in the urine.

Study Design: We will recruit N=5 adult subjects with neuropathic bladder due to SCI or SB.

Clinical Setting: MedStar National Rehabilitation Hospital

The Impact of Self-Management with Probiotics on Urinary Symptoms and the Urine Microbiome in Individuals with Spinal Cord Injury and Spina Bifida Protocol

5/18/2017

Page 1 of 17

Target Enrollment: 5 subjects at least 18 years of age with SCI or SB and at least 1-year post-injury (if SCI).

Informed Consent: Consent will be obtained by the PI, Study Coordinator, or Research Assistant.

Inclusion Criteria: Inclusion criteria for safety study participants are: 1) age 18-50 years; 2) if SCI, at least 1-year duration; 3) neuropathic bladder, as determined by the attending physician; 4) utilizing intermittent catheterization for bladder management; and 5) community dwelling.

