Baseline Data Collection: At baseline, subjects who do not report urinary symptoms (see below) other than cloudy or foul-smelling urine will complete the validated USQ-NB. Urine will be collected for urinalysis and urine culture (see below for methods of urine collection), however urinalysis results will be used for post hoc data collection only and not inclusion/exclusion in keeping with the recommendations of the IDSA.

Intervention: Eligible patients will undergo 1 *Lactobacillus* (Culturelle GG, 20 Billion live organisms) instillation by study personnel at the study site. For the intravesicular *Lactobacillus* instillation, the contents of 1 *Lactobacillus* capsule will be mixed into 45 cc sterile 0.9% saline (adult bladder volume is 450cc, so this amount represents 10% of adult bladder volume). After mixing, study personnel will draw up the 45 cc of the liquid *Lactobacillus* mixture into a 60cc catheter tip syringe and instill via the intermittent catheter. Participants will be observed in the clinic for 30 minutes after instillation to assure that no adverse reactions occur.

Post-Intervention Follow-Up: After completion of the one *Lactobacillus* instillation and 30 minute observation period, participants will be asked to monitor for any symptoms using the USQ-NB daily for one week. They will be instructed to contact study personnel in the event of any urinary symptoms. They will then return to the clinic 5-10 days after instillation for repeat urinalysis and urine culture.

Phase 1b: Safety study of single bladder instillation probiotic in children with SB or SCI. After Phase 1a is complete, accumulated safety data (inclusive of adverse events and laboratory results)

The Impact of Self-Management with Probiotics on Urinary Symptoms and the Urine Microbiome in Individuals with Spinal Cord Injury and Spina Bifida Protocol

5/18/2017

Page 2 of 17

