If participants instill *Lactobacillus* at any time during the intervention phase, and after *Lactobacillus* instillation reports a UTI as an Adverse Event (AE) we will request their urinalysis and urine culture results to attempt to determine if *Lactobacillus* might have been the cause of the UTI. If determined necessary by the PI, Co-PI and/or DSMB other AEs reported could require retrieval of medical records.

Phase III: Pilot Study of Multiple (up to 2) *Lactobacillus* Bladder Instillations

We will recruit 30 persons in whom we will collect urine up to 18 timepoints (up to monthly for the first year when not experiencing symptoms, up to two times when subject experience urinary symptoms, follow-up after either *Lactobacillus* treatment or antibiotics, and three (3) months into the six (6) months follow-up) in order to **estimate the strength of the associations between successful implementation of the probiotic self-management program and urinary symptoms, bladder inflammation, and the urine microbiome.** We will conduct an 18-month study in which each participant will serve as his/her own control through 3 phases of study: 6-months usual care (baseline), 6-months probiotic intervention, and 6-months follow-up
Study Design: We will recruit N=30 subjects with neuropathic bladder who will contribute urine samples for analyses.

Clinical Setting: MedStar National Rehabilitation Hospital and Children's National Medical Center.

Target Enrollment: 30 adult subjects at least 1-year post-injury and 18 years of age with SCI/MS or at least 18 years of age with SB

Recruitment Strategy: SCI/MS and SB subjects will be enrolled with assistance from United Spinal Association. Additionally, we will query the MedStar National Rehabilitation Hospital inpatient service, the 40+ MedStar National Rehabilitation Network outpatient sites, various MedStar Network databases, and the CNMC Spina Bifida database. Databases will be queried for participants who meet the eligibility criteria and have already provided HIPAA authorization and consent to be contacted for future research. Announcements and IRB-approved flyers will be posted on the United Spinal Association and study websites and at participating institutions.

Informed Consent: Consent will be obtained by the PI, Study Coordinator, or Research Assistant. All project staff are currently CITI certified and have passed all requirements for HIPAA certifications.

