following urinary symptoms is required for UTI diagnosis in patients using intermittent catheterization: new onset or worsening fever, rigors, altered mental status, malaise, lethargy with no other identified cause, flank pain, costovertebral angle tenderness, acute hematuria, pelvic discomfort, increased spasticity, autonomic dysreflexia or sense of unease. The Guidelines specifically state that “the presence or absence of odorous or cloudy urine should NOT be used as an indication for urine culture or antimicrobial therapy” and “the presence, absence or degree of pyuria should NOT be interpreted as an indication for antimicrobial treatment.” If a subject presents with any of these symptoms and there are $\geq 10^3$ cfu/hpf bacterial growth on urine culture, the subject will be excluded and treated for a UTI according to clinical best practice.

Participant Burden:

Urine samples for urinalysis, urine culture and metagenomic sequencing will be obtained at up to monthly for the first year of study participation when not experiencing symptoms, at up to 2 occurrences of urinary symptoms during SMP_{PRO} intervention phase, and follow-up after either lactobacillus treatment or antibiotics and at follow-up, for a total of up to 18 samples per patient depending on the frequency with which urinary symptoms are experienced. When possible, our Research Assistant will meet with the patient at a mutually convenient location.

Baseline Data Collection:

Per IRB protocol # 2014-211 phase II, after consent, participants will complete the Health History Questionnaire, Urinary Symptom Questionnaire, In addition to questionnaires, all participants will provide a urine sample using sterile catheterization techniques. Thereafter, participants will complete the Urinary Symptom Questionnaire weekly.

Intervention:

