After 6 months of baseline data collection the intervention phase will begin. Prior to implementing the intervention protocol, participants will provide study staff with a urine sample either at MedStar NRH, CNMC, or when possible, the study RA will meet with the participant at a mutually convenient location. After urine sample is collected, study participants will follow the study protocol and complete USQ-NB weekly. If/when urinary symptoms occur, they will be instructed to follow the SMP_{PRO} protocol to determine whether to initiate intravesicular *Lactobacillus* instillation or be evaluated by a physician. The self-management protocol (SMP_{PRO}) will also direct them to discontinue *Lactobacillus* instillation or be evaluated by a physician if symptoms remit, persist or worsen. If participants are directed by the self-management protocol to seek medical attention or s/he feels the need for medical evaluation, s/he will be advised to obtain care as they typically would by their health care provider. Participants will be supplied with letters to be brought to their health care provider notifying them of the study and requesting sharing of urinalysis and urine culture results with the research team. A verified UTI will include those that resulted in antibiotic treatment by a health care professional. An additional urine sample for metagenomics will either be left with the health care provider for pick up by the research team, brought to the research site, or obtained by the RA at a mutually convenient site. If participant is treating urinary symptoms at home with *Lactobacillus*, a urine sample will be dropped off either at MedStar NRH, CNMC or when possible, the study RA will meet with the participant at a mutually convenient location.

The Impact of Self-Management with Probiotics on Urinary Symptoms and the Urine Microbiome in Individuals with Spinal Cord Injury and Spina Bifida Protocol

5/18/2017

Page 8 of 17

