For the intravesicular *Lactobacillus* instillation, the contents of 1 *Lactobacillus* capsule will be mixed into 45 cc sterile 0.9% saline (adult bladder volume is 450cc, so this amount represents 10% of adult bladder volume). After mixing, study personnel will draw up the 45 cc of the liquid *Lactobacillus* mixture into a 60cc catheter tip syringe and instill via the intermittent catheter. For children volume is based on age (see table on page 4 of protocol). Study participant will recheck symptoms after 24 hrs (valid range 22-30 hrs) following the SMP_{PRO} protocol and either complete another *Lactobacillus* instillation or seek medical attention. If symptoms still persist 4 hrs after second instillation, study participants should seek medical attention.

Post-Intervention Follow-Up:

After completion of the 6-month patient-initiated self-management protocol intervention period, participants will monitor symptoms weekly using the USQ-NB. At the end of follow-up, we will obtain another urine sample from all participants.

Measurements:

In addition to the measurements described in Phase II the following measurements will occur for phase III;

Urine Acquisition: A 50-100 ml urine sample will be collected from each subject for (1) urinalysis and cultivation, and (2) urine microbiome by SMRT sequencing. Urine will be collected from a new, unused intermittent catheter.

Urine Preparation: Collected urine will be immediately placed at 4°C. Within 6 hours, samples will be taken to CNMC for sequencing preparation. At CNMC, urine samples will be centrifuged at 4°C, 5,000 x g for 20 minutes. The supernatant will be aliquoted in 2 ml cryotubes and frozen at -20°C. 10ml PBS will be added to the pellet with the remaining supernatant and then centrifuged (5,000xg) at 4°C for 20 minutes. The pellets and aspirated PBS wash solution will be stored at -20°C. Pellets will later be transferred for DNA isolation and SMRT sequencing.

Urinalysis: Urine samples will be assessed utilizing standard clinical microbiology semiquantitative chemical testing using commercial disposable test strips for glucose, bilirubin, ketone, specific gravity, blood pH, protein, urobilinogen, nitrite, and leukocyte esterase. After centrifuging for 5 minutes, microscopic examination for and quantification of WBCs, RBCs, epithelial cells, yeast, bacteria, *Trichomonas vaginalis*, sperm cells, mucous filaments and crystals will be performed using standard microbial techniques.

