To determine whether bacterial diversity differs between study groups the Shannon Diversity Index will be used. The Shannon Index is a measure of sample diversity that takes into account total number of bacterial types in the sample and relative proportion of the bacterial types. From the subsample of 50 participants giving urine samples, subjects who did in fact utilize the SMP at least once during the 6-month SMP time frame will be stratified into two groups, those who responded to SMP and those who did not; we will define "response" as the observation of a 10% or more decrease in the average number of USQ items endorsed within any time frame, so that each of the 50 persons in this sub-sample will be characterized as either a responder (10% or more decrease) or a non-responder (0-9.99% decrease). A scatter plot of response group versus Shannon Index will be produced, and a mixed effects linear regression model will test the individual (main) and interaction effects of response group and time on Shannon Index. A positive time coefficient is indicative of increased microbiome diversity and a negative time coefficient indicates reduces diversity. The magnitude of difference between the response groups will be determined using the Yue-Clayton theta similarity index (θ). The θ index measures the difference in the number and relative abundance of bacterial species between samples^{4,5} when $\theta=1$ two samples have identical community structure and when $\theta=0$ indicates complete dissimilarity between samples. Pathoscope will be used to calculate abundance of different taxonomic groups at each time point.

REFERENCES

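### H4 keeps reads from the instilled Lactobacillus in Shannon and theta and leaves sampling time unspecified, so residual product can pass for a change in the native microbiome

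*Combined protocol and SAP*

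**What the plan says.** The opening paragraph of Phase III lists the urine timepoints. They include samples "up to two times when subject experience urinary symptoms, follow-up after either" Lactobacillus treatment or antibiotics. Participant Burden sends these samples for metagenomic sequencing and repeats the list: "follow-up after either lactobacillus treatment or antibiotics and at follow-up, for a total of up to 18 samples per patient". Under Phase III, Intervention, a participant treating symptoms at home with Lactobacillus is also to provide urine: "a urine sample will be dropped off either at MedStar NRH, CNMC or when possible" handed to the research assistant elsewhere. None of these places puts the episode sample before the first instillation or sets an interval between instillation and the later sample. The same section does ask for urine before the intervention starts, but that is one sample at the opening of the 6-month phase, not one per episode.

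SMRT Sequencing Methods extracts DNA from all pelleted bacteria and amplifies it with universal 16S primers. H4 then discards low-quality, short and chimeric reads and classifies everything that is left. Shannon is modelled on response group, time and their interaction. The reading of the time effect is fixed in advance: "A positive time coefficient is indicative of increased microbiome diversity and a negative time coefficient indicates reduces diversity". Theta is used to express the difference between response groups. H4 also has Pathoscope report the abundance of taxonomic groups at each time point.

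**The concern.** The intervention is itself a large dose of bacteria placed in the organ whose bacteria are then sequenced. A sample taken soon after an instillation contains the participant's own community plus some product, and H4 treats the sum as the participant's microbiome. Samples from the first six months cannot contain study product, so any contamination falls on one side of the time contrast.

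The protocol recognises the premise. Phases Ia and 1b both ask whether the instilled organism "persists in the urine". H4 makes no use of the answer. At stake is whether a time coefficient can be read as an effect of self-management on the native bladder community or merely shows that product had not yet cleared.

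**Working it through.** **The plan's own figure.** The only quantitative design figure for H4 is the number of SMRT cells per sample: 189 × 1 × 87 / 30,000 = 0.548, rounded up to 1. It reproduces. It makes no allowance for product reads. If a share p of reads is product, the same formula needs 0.548 / (1 − p) cells for the native species: 1.10 at p = 50% and 5.48 at p = 90%, against 1 planned.

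**Effect on Shannon.** Take the product as one taxon absent from the native community, hold that community fixed, and let p be the product share of reads. In natural logs:

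H′ = (1 − p)H + h(p), with h(p) = −p ln p − (1 − p) ln(1 − p).

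For native H = 1.0:

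- p = 0.3: 0.7 × 1.0 + 0.611 = 1.31 (+31%)
- p = 0.9: 0.1 × 1.0 + 0.325 = 0.43 (−57%)

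Two fuller native profiles give the changes in the table. Profile A has 189 species with a most-to-least abundance ratio of 87 (both from SMRT Sequencing Methods) and a geometric shape (assumed); H = 4.678. Profile B has one organism at 80% and 19 sharing 20% (assumed); H = 1.089.

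| p | Change in H, A | Change in H, B |
|---|---|---|
| 10% | −0.143 | +0.216 |
| 50% | −1.646 | +0.149 |
| 90% | −3.885 | −0.655 |

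Shannon rises at small p and falls at large p. The sign turns at about 2.5% for A and 61% for B. With product reads removed and the rest renormalised, H returns to 4.678 and 1.089 at every p.

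**Effect on the interaction.** The shift is H′ − H = h(p) − pH. If both response groups have the same p and the same native H, the shifts cancel. If p is equal but native H differs, they do not. At p = 0.5, H = 1.0 reads 1.19 (+0.19) and H = 2.0 reads 1.69 (−0.31), a false interaction of 0.5.

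**Effect on theta between groups.** θ = Σab / (Σa² + Σb² − Σab). Two groups with identical native communities should give 1. With product shares of 10% and 50% they give 0.255 (A) or 0.563 (B). With equal shares they still give 1, and where the native communities differ, an equal share pulls theta towards 1.

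**How large p might be.** The documents do not say. As an illustration, assume one dose of 20 billion, 100 ml of urine, a native load of 10⁵/ml, 10% left after each emptying and no growth. After k emptyings, product per ml is 20 × 10⁹ × 0.1^k / 100, and p is that figure divided by itself plus 10⁵:

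- 1 emptying: 99.5%
- 2 emptyings: 95%
- 4 emptyings: 17%
- 6 emptyings: 0.2%

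The result depends heavily on the assumptions. After 4 emptyings p is about 1% if 5% is left each time and 94% if 30% is left. With 10% left, p is 95% for a native load of 10³/ml and 0.2% for 10⁷/ml.

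The count of 20 billion is stated for Phase Ia and appears against 45 ml in the Phase 1b volume table. Phase III says only one capsule in 45 cc, so its count is inferred. The Shannon and theta results do not use it.

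**The case against.** **Most samples may be clean.** Many of the up to 18 samples are not tied to an instillation: the first six months precede any product, the monthly samples are taken when symptom-free, and one falls in follow-up. H4 does not define time or say that episode samples enter the model, and H2 uses only samples at the start of each timeframe. The Phase III opening also lists symptom samples separately from follow-up samples, so the former could be meant as pre-treatment. This stands as a limit on size. It does not close the gap, because no section states the order, and nothing keeps a monthly sample in months 7 to 12 away from a recent instillation.

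**Theta and the interaction are not automatically biased.** This is correct. A reader might infer that theta collapses because post-dose urine is compared with the same person's pre-dose urine. The plan makes no such comparison. Theta is between response groups, all of whom used the self-management protocol at least once, so distortion needs the groups to differ as described above or, for theta, an equal share that masks a real difference.

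**It can be repaired later.** A reader might infer that the artefact would be beyond correction. That is not so: H4 tabulates each organism's proportion, so product would be visible and the reads could be filtered afterwards. What could not be recovered is unrecorded timing. The weekly tablet count in Phase II places use only to the week, and the data and safety section asks for instillation timing only within adverse-effect reports. A filter chosen after seeing results would also be post hoc.

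**The total community is a legitimate target.** This also stands. Persistence is a study question, and the plan's sentence about the time coefficient is literally true of all bacteria present. That argues for reporting both versions, not for replacing one with the other.

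**Conclusion.** The point holds as an unaddressed route to bias of unknown size. In samples taken soon after an instillation, residual product alone can raise or lower Shannon with the native community unchanged, so the sign of the time coefficient cannot by itself be read as a native change. The time effect is directly exposed; the interaction and theta are exposed conditionally.

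The illustration of 1.31 or 0.43 against a native 1.0 rests on an unchanged native community, a single product taxon absent from it, and product shares of 30% and 90% chosen for illustration. Under simple washout the effect fades within several catheterisations; persistence or growth would prolong it.

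A reader might go further and conclude that H4 merely measures its own inoculum. The documents do not support that, since the product share is unknown and many samples may carry none. H4 is a secondary outcome of a pilot with no stated alpha, which limits the weight of the point, but the correction is cheap.

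**What to change.** 1. In H4, pre-specify Shannon and theta in two versions: all reads, and reads assigned to the product strain or species removed with the rest renormalised. Report product abundance as a separate outcome. State that a time coefficient will not be interpreted as a change in the native microbiome unless the product-removed version agrees.
2. In the Phase III timepoint list, Participant Burden and Intervention sections, record the date and time of every urine sample and of the last instillation. Collect the symptom-episode sample before that episode's first instillation where feasible. In the analysis, flag samples by time since instillation or adjust for it, and define which samples make up the time variable.

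The cost is SAP wording, one filtering step on reads already planned, and a collection-time instruction; dosing and treatment rules are untouched. H4 describes Pathoscope as able to classify to subspecies level, but whether it can separate the product strain in these data should be checked. If only species-level removal is possible, it also takes out native strains of that species and any colonisation effect; the all-reads version and the abundance outcome still show both. Some episode samples will still be taken after instillation, and the recorded times identify them.

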H2. Compared with usual management, self-management of urinary symptoms with probiotics will reduce bladder inflammation (Secondary outcome). For those 20 participants in the subsample giving urine samples, bladder inflammation will be measured from each urine sample using a standard white blood count (WBC) from the urinalysis. WBC counts will be obtained only at the start of each timeframe, and so can be analyzed longitudinally as continuous variables representing the 6-month pre-treatment period and the 6 month-SMP_{PRO} period. As such we plan a mixed effects linear regression model of WBC counts with time treated as the factor of interest. This analysis will assess whether WBC is significantly different from the SMP_{PRO}, and post-SMP_{PRO}, relative to the baseline pre-treatment periods.

H3. Compared with usual management, self-management of urinary symptoms with probiotics will reduce the need for antibiotics to treat UTI (Secondary outcome). The number of times antibiotics are used for each patient will be obtained from their medical records or self report. This value will be analyzed with the same three-point longitudinal mixed effects regression model with time as the factor of interest. Depending on the distribution of the outcome (i.e. given the count nature of this outcome, it may be Poisson distributed), we will utilize either linear or Poisson regression models. This analysis will assess whether there is an association between UTI rate during use of the SMP_{PRO}, and post-SMP_{PRO} exposure, relative to UTI rate during the baseline pre-treatment period.

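### Yue-Clayton theta between responders and non-responders has no within-group reference, so the figure cannot be read as a group effect on the microbiome

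*Combined protocol and SAP*

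**What the plan says.** The text is in the Combined protocol and SAP, under H4 (microbiome, secondary outcome). Participants in the urine subsample who used the self-management protocol at least once "will be stratified into two groups, those who responded to SMP and those who did not". Two comparisons of these groups follow.

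- **Diversity.** "a mixed effects linear regression model will test the individual (main) and interaction effects of response group and time on Shannon Index".
- **Composition.** "The magnitude of difference between the response groups will be determined using the Yue-Clayton theta similarity index". The index is then described: "The θ index measures the difference in the number and relative abundance of bacterial species between samples". The only reference points are the ends of the scale: at θ = 1, "two samples have identical community structure and when $\theta=0$ indicates complete dissimilarity between samples".

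The plan does not say how theta, a value for a pair of samples, becomes one value for two groups. It could be an average over cross-group pairs, or theta between two pooled profiles, at one time point or over all of them. The rest of H4 covers sequence processing and taxonomic classification. No section gives a within-group theta, a confidence interval, a threshold or a test for theta.

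**The concern.** People differ in their urinary flora whether or not they respond. Theta between a responder and a non-responder contains all of that ordinary variation plus any effect of group, and the plan offers nothing that separates the two. If the only yardstick is θ = 1, a value such as 0.12 looks like a large difference between groups when it may show only how much any two participants differ.

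Theta is the plan's only stated measure of how far composition differs between the groups. A misread value would pass into the account of who responds to intravesical *Lactobacillus* and into the planning of later studies.

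**Working it through.** The plan states no theta value, threshold or power for H4, so there is no figure to reproduce. The check asks what theta would be if the groups did not differ at all.

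**Inputs from the document**
- 189 species and a ratio of 87 between the most and least abundant (Phase III, SMRT Sequencing Methods).
- Urine subsample of 30 (Phase III), 20 (H2: "For those 20 participants in the subsample giving urine samples") or 50 (H4: "From the subsample of 50 participants giving urine samples"). The inconsistency is a separate matter; all three sizes were run.

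**Assumptions (not in the document)**
- Mean abundances fall geometrically from 87 to 1.
- Each person's composition is drawn from one Dirichlet distribution with these means, the same for both groups. Concentration c runs from 5 (people very different) to 1000 (people nearly alike).
- Equal groups, one sample per person, 30,000 reads per sample, 200 runs per setting.

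**Formula.** For compositions a and b,

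θ = Σab / (Σa² + Σb² − Σab).

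**Closed-form approximation.** Let q be the sum of squared mean abundances; here q = 0.012147. For two different people the expected Σab is q, and the expected Σa² is A = (cq + 1)/(c + 1). Then θ ≈ q/(2A − q).

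- c = 5: A = (0.060735 + 1)/6 = 0.176789; θ ≈ 0.012147/(0.353578 − 0.012147) = 0.036.
- c = 1000: A = (12.147 + 1)/1001 = 0.013134; θ ≈ 0.012147/(0.026268 − 0.012147) = 0.86.

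For pooled profiles with n people per group, replace A by q + (A − q)/n. With c = 5 and n = 15 this is 0.012147 + 0.164642/15 = 0.023123, so θ ≈ 0.012147/(0.046246 − 0.012147) = 0.36.

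Group membership appears nowhere in the pairwise expression, so it applies equally to within-group and cross-group pairs of different people.

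**Simulation, no group difference, 15 v 15**

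| Concentration c | Cross-group pairs | Within-group pairs | Pooled group profiles |
|---|---|---|---|
| 5 | 0.041 | 0.042 | 0.353 |
| 20 | 0.121 | 0.121 | 0.661 |
| 100 | 0.387 | 0.386 | 0.905 |
| 1000 | 0.856 | 0.856 | 0.989 |

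**Effect of sample size.** Cross-group pair theta barely moves with total N (0.041 at N = 20, 30 and 50 for c = 5). Pooled-profile theta does move: 0.27, 0.35 and 0.48 for c = 5, and 0.86, 0.91 and 0.94 for c = 100. On the pooled reading the apparent magnitude would depend on enrolment.

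**Does a reference remove the problem?** A permutation test of within-group minus between-group theta rejected in 1.5% to 6% of null runs at the 5% level. This covers 15 settings (three sizes; c = 1, 5, 20, 100 and 1000). With 200 runs the Monte Carlo standard error is √(0.05 × 0.95/200) = 1.5 percentage points, so these rates are compatible with the nominal level.

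**The case against.** The strongest reply is that the plan calls theta a magnitude and attaches no cut-off, decision rule or claim to it. The formal group test is the mixed model on the Shannon Index. This is also a secondary outcome in a pilot meant to estimate associations, and the matter can be settled at analysis.

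Much of this stands, and it rules out three stronger readings that a reader might infer.

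- *That the study would declare the groups different whatever the truth, or that type I error is inflated.* No test or threshold is tied to theta, so there is no formal error rate to inflate. With little person-to-person variation, or with pooled profiles, null theta can be 0.86 to 0.99 and would not look dissimilar.
- *That H4 as a whole fails.* H4 concerns return of the microbiome to baseline. The responder comparison is one part of its analysis, and diversity has its own model.
- *That the plan's within-group average is distorted by repeated samples from the same person.* The plan contains no within-group average. Same-person pairs are something to avoid when adding one.

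The reply does not remove the gap. The Shannon Index summarises diversity inside one sample, and two communities can have equal Shannon values and share no species. Leaving theta descriptive does not help either: a described magnitude still has to measure what it is said to measure.

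**Conclusion.** The point holds as a fault in a descriptive measure for a secondary outcome. Followed as written, the plan yields a theta that mixes person-to-person variation with any group effect, and it gives no means of separating them.

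The direction needs only that participants differ from one another. The size rests on the assumed Dirichlet range, the geometric abundance profile and equal groups; the document gives none of these. Over that range, with 15 per group, null theta is 0.04 to 0.86 for cross-group pairs and 0.35 to 0.99 for pooled profiles. The true range in this population could be narrower. The analysis is limited to participants who used the protocol and the plan gives no responder split, so real groups may be smaller or unequal.

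The primary outcomes and safety are unaffected. The change is worth making because it is cheap and uses data already being collected.

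**What to change.** Amend the H4 text as follows.

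1. State which sample pairs and time points enter theta.
2. Work within each study period and sample type (asymptomatic, symptomatic, post-treatment), with one composition per person, and name the rule for obtaining it where a person has several samples of that type. Merging all samples in a period would lose the contrast between symptomatic and asymptomatic urine that Phase III sampling is set up to capture.
3. Report mean between-group theta beside mean within-group theta, the latter from pairs of different people only, and report the difference between them.
4. Test that difference by permuting response labels at person level.
5. Do not interpret between-group theta on its own. Because response is defined by outcome and not randomised, describe any difference as an association.

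The cost is a few lines of SAP text and code, with no new data or visits. The downside is small: a little more analysis, and sparse sample types may leave few pairs, so some contrasts may only be describable.
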